7.6. Analysis of Exploratory Efficacy Parameters

7.6.1. Exploratory Efficacy Analysis

Similar to the secondary efficacy endpoints, all exploratory efficacy analyses will be conducted based on the FAS population during the treatment period (double-blind and treatment extension periods).

Mean, change (if applicable) from baseline, and percentage change (if applicable) from baseline will be summarized by treatment and visit using descriptive statistics for the following:

- WHO-5 Total Score
- TSQM Subscales (Effectiveness, Convenience, Overall satisfaction)
- VitiQoL Total scales and Subscales
- HADS Anxiety and Depression scores

Categorical endpoints at postbaseline visits will be summarized by treatment and visit using descriptive statistics, including the following:

- F-PhGVA and T-PhGVA
- F-PaGIC-V and T-PaGIC-V
- Color-matching question

- Proportion of participants achieving T-PhGVA response
- Proportion of participants achieving F-PhGVA response
- Proportion of participants achieving F-PaGIC-V response
- Proportion of participants achieving T-PaGIC-V response

7.7. Pharmacokinetic Analyses

Trough plasma concentrations of ruxolitinib at all study visits will be summarized using descriptive statistics by treatment group.

7.8. Pharmacodynamic Analyses

Biomarkers from serum samples will be summarized by descriptive statistics by treatment group. The purpose of these analyses will be to retrospectively evaluate changes in disease related biomarkers (eg, CXCL9, CXCL10, IL-15, IFN-gamma) at baseline before drug administration and at Weeks 12, 24, 40, and 52.

7.9. Pharmacokinetic/Pharmacodynamic Analyses

A basic linear or Emax model may be evaluated to characterize changes in disease related biomarkers (eg, CXCL9, CXCL10, IL-15, IFN-gamma) from baseline and as a function of plasma ruxolitinib steady-state exposures (C_{min}).

8. SAFETY AND TOLERABILITY

[Appendix A](#) provides a list of planned tables, figures, and listings. Sample data displays are included in a separate document.

8.1. General Considerations

The analyses in this section will be provided for the safety population in the DB period and the TE evaluable population in TE period. Cumulative TEAEs across the treatment periods (DB and TE period) will be summarized. In addition, summaries of exposure-adjusted TEAEs will be provided based on the actual treatment received.

Summary tables may be replaced with listings when appropriate. For instance, an AE frequency table may be replaced with a listing if it only contains a few unique PTs reported on relatively few participants.

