4. STUDY DESIGN

4.1. Overall Design

This is a randomized, vehicle-controlled study in adolescent and adult participants (age ≥ 12 years) with non-segmental vitiligo who have depigmented area including $\geq 0.5\%$ BSA on the face, ≥ 0.5 F-VASI, $\geq 3\%$ BSA on nonfacial areas, ≥ 3 T-VASI, and for whom total body involved vitiligo area (facial and nonfacial) does not exceed 10% BSA. Approximately 300 participants will be randomized 2:1 to receive initial study treatment (ruxolitinib cream 1.5% BID:vehicle) for 24 weeks (see [Figure 1](#)). Participants will be stratified by region (North America or Europe) and skin type (Fitzpatrick scale Type I and II vs Type III, IV, V, and VI). Adolescents (≥ 12 to < 18 years) will make up at least 10% of the study population, and no more than 50% of participants will be > 40 years old.

During the double-blind, vehicle-controlled period, participants will receive ruxolitinib cream 1.5% BID or vehicle for 24 weeks to be applied to depigmented areas only on the face and body up to 10% total BSA. Participants should continue to treat depigmented areas identified for treatment at baseline even if the area begins to improve or fully repigment.

After completion of the Week 24 assessments, participants will be offered the opportunity to continue in the treatment extension period. Participants initially randomized to vehicle will be crossed over to active drug, and participants treated with ruxolitinib cream will receive an additional 28 weeks of treatment with ruxolitinib cream 1.5% BID. To be eligible for the treatment extension, participants must have completed the baseline and Week 24 visit assessments, be compliant with study procedures, and not have any safety issues. During the treatment extension, participants should continue to treat depigmented areas identified for treatment at baseline even if the area begins to improve or fully repigment. Total treated areas (facial and nonfacial areas) should not exceed to 10% BSA.

Safety endpoints, such as nature of AEs (type, frequency, and severity), vital signs, targeted physical examination, and routine laboratory investigations, will be monitored and recorded throughout the course of this study.

Following the last application of ruxolitinib cream at Week 52, there will be a 30-day safety follow-up period to evaluate safety and duration of response.

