6. STUDY TREATMENT

6.1. Study Treatment Application

[Table 9](#) presents the study treatment information.

Table 9: Study Treatment Information

Study treatment name:	Ruxolitinib	Vehicle
Dosage formulation:	Cream	
Unit dose strength(s)/dosage level(s):	1.5%	Not applicable
Route of administration:	Topical	
Administration instructions:	Double-blind and treatment extension periods: BID. A thin film is applied to depigmented vitiligo areas.	Double-blind period: BID. A thin film is applied to the depigmented vitiligo areas. Treatment extension period: Not applicable.
Packaging and labeling:	Ruxolitinib cream and vehicle cream will be provided in 60 g tube. Each tube will be labeled as required per country requirement.	
Storage:	Ambient (15°C-30°C/59°F-86°F)	
Status of treatment in participating countries:	Investigational	Not applicable

On visit days, study drug will be applied in the clinic during the visit. Participants should remove study drug from the tube in fingertip units until all of the areas to be treated are covered by a thin film; the tube will be weighed before and after application to determine the participant's dosage. On the day of a visit, the participant should not apply the study drug at home and will apply study drug from the new kit in the clinic. Participants will be instructed to document treated areas and advised to limit use to no more than one 60 g tube per week. Application instructions will be provided by the site study staff, and the participants will record their daily applications via a diary card given to the participants during each study visit. Refer to the Study Pharmacy Manual for participant instructions for handling study of drug.

At any time, if vitiligo areas become significantly more extensive than from the previous visit, the participant should contact the study site to discuss with the investigator whether additional evaluation at the clinic is required. If any other skin products that are permitted under the study Protocol are used, participants should continue these unchanged during the study.

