1. INTRODUCTION

INCB 18424-306 is a randomized, vehicle-controlled study in adolescent and adult participants (age \geq 12 years) with nonsegmental vitiligo who have depigmented area including \geq 0.5% BSA on the face, \geq 0.5 F-VASI, \geq 3% BSA on nonfacial areas, \geq 3 T-VASI, and for whom total body involved vitiligo area (facial and nonfacial) does not exceed 10% BSA. Approximately 300 participants will be randomized 2:1 to receive initial study treatment (ruxolitinib cream 1.5% BID:vehicle; applied to depigmented vitiligo areas on the face and body up to 10% total BSA) for 24 weeks. Participants will be stratified by region (North America or Europe) and skin type (Fitzpatrick scale Type I and II vs Type III, IV, V, and VI). Adolescents (\geq 12 to $<$ 18 years) will make up at least 10% of the study population, and no more than 50% of participants will be $>$ 40 years old.

After completion of the Week 24 assessments, participants will be offered the opportunity to receive an additional 28 weeks of treatment extension with ruxolitinib cream 1.5% BID. To be eligible for the treatment extension, participants must have completed the baseline and Week 24 visit assessments, be compliant with study procedures, and not have any safety issues. The total treated area should not exceed 10% BSA (facial and nonfacial).

Participants who successfully complete the 52-week treatment in this study may be eligible to participate in a separate extension study to evaluate durability of effect and maintenance regimens.

The purpose of this SAP is to provide details of the statistical analyses that have been outlined in the study Protocol. The scope of this plan will be executed by the Department of Biostatistics or designee, and the analyses of PK will be executed by the Department of Clinical Pharmacokinetics or designee.

Another Phase 3 study, INCB 18424-307, has the identical study design as INCB 18424-306. This SAP applies to both INCB 18424-306 and INCB 18424-307 studies.

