3.1. Randomization

Approximately 300 participants will be randomized 2:1 to receive initial study treatment (ruxolitinib cream 1.5% BID:vehicle) for 24 weeks. Participants will be stratified by skin type (Fitzpatrick scale Type I and II vs Type III, IV, V, and VI) and region (North America or Europe).

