2.9.4	Summary of WHO-5 During Treatment Period	FAS
2.9.5	Summary of TSQM During Treatment Period	FAS
2.9.6	Summary of VitiQoL During Treatment Period	FAS
2.9.7	Summary of HADS During Treatment Period	FAS
Exposure & Compliance		
3.1.1.1	Summary of Exposure in Double-Blind Period	Safety
3.1.1.2	Summary of Exposure in Treatment Extension Period	TE
3.1.1.3	Summary of Exposure in During Treatment Period	Safety
3.1.2.1	Summary of Study Drug Compliance in Double-Blind Period	Safety
3.1.2.2	Summary of Study Drug Compliance in Treatment Extension Period	TE
3.1.2.3	Summary of Study Drug Compliance in During Treatment Period	Safety
Adverse Events		
3.2.1.1.X	Overall Summary of Treatment-Emergent Adverse Events	Safety
3.2.1.1.Y	Overall Summary of Exposure-Adjusted Treatment-Emergent Adverse Events	Safety
3.2.2.1.X	Summary of Treatment-Emergent Adverse Events by MedDRA System Organ Class and Preferred Term	Safety
3.2.3.1.X	Summary of Treatment-Emergent Adverse Events by MedDRA Preferred Term in Decreasing Order of Frequency	Safety
3.2.3.1.1.X	Summary of Treatment-Emergent Adverse Events $\geq 1\%$ in Any Treatment Group by MedDRA Preferred Term in Decreasing Order of Frequency	Safety
3.2.3.1.2.X	Summary of Application Site Reactions by MedDRA Preferred Term in Decreasing Order of Frequency	Safety
3.2.3.1.Y	Summary of Treatment-Emergent Adverse Events With Vehicle Group by MedDRA Preferred Term in Decreasing Order of Frequency During the Treatment Period	Safety
3.2.3.1.1.Y	Summary of Treatment-Emergent Adverse Events $\geq 1\%$ in any Treatment Group With Vehicle Group by MedDRA Preferred Term in Decreasing Order of Frequency During the Treatment Period	Safety
3.2.3.1.2.Y	Summary of Application Site Reactions With Vehicle Group by MedDRA Preferred Term in Decreasing Order of Frequency During the Treatment Period	Safety
3.2.3.1.3.Y	Summary of Exposure-Adjusted Incidence Rates of Treatment-Emergent Adverse Events With Vehicle Group by MedDRA Preferred Terms in Decreasing Order of Frequency During the Treatment Period	Safety
3.2.3.1.4.Y	Summary of Exposure-Adjusted Incidence Rates of Treatment-Emergent Adverse Events $\geq 1\%$ in Any Treatment Group With Vehicle Group by MedDRA Preferred Term in Decreasing Order of Frequency During the Treatment Period	Safety
3.2.3.1.5.Y	Summary of Exposure-Adjusted Incidence Rates of Application Site Reactions With Vehicle Group by MedDRA Preferred Term in Decreasing Order of Frequency During the Treatment Period	Safety

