Note: For AE tables ending with "Y", tables will be provided for the treatment period (double-blind and treatment extension periods). For participants who cross over, he/she should be included in both treatment groups.

Note: For Laboratory Values/Vital Sign tables ending with "X", separate tables will be provided for the double-blind period and treatment extension period.

Figure

Figure No.	Title	Population
4.1.1	Proportion of Participants Achieving F-VASI75 During Treatment Period	FAS
4.1.2	Proportion of Participants Achieving F-VASI25 During Treatment Period	FAS
4.1.3	Proportion of Participants Achieving F-VASI50 During Treatment Period	FAS
4.1.4	Proportion of Participants Achieving F-VASI90 During Treatment Period	FAS
4.1.6	Mean and Standard Error Plot of F-VASI During Treatment Period	FAS
4.1.7	Mean and Standard Error Plot of Change From Baseline in F-VASI During Treatment Period	FAS
4.1.8	Mean and Standard Error Plot of Percent Change From Baseline in F-VASI During Treatment Period	FAS
4.1.9	Forest Plot of Response Rate Difference in Achieving F-VASI75 at Week 24	FAS
4.2.1	Proportion of Participants Achieving T-VASI75 During Treatment Period	FAS
4.2.2	Proportion of Participants Achieving T-VASI25 During Treatment Period	FAS

Figure No.	Title	Population
4.2.3	Proportion of Participants Achieving T-VASI50 During Treatment Period	FAS
4.2.4	Proportion of Participants Achieving T-VASI90 During Treatment Period	FAS
4.2.6	Mean and Standard Error Plot of T-VASI During Treatment Period	FAS
4.2.7	Mean and Standard Error Plot of Change From Baseline in T-VASI During Treatment Period	FAS
4.2.8	Mean and Standard Error Plot of Percent Change From Baseline in T-VASI During Treatment Period	FAS
4.3.1	Mean and Standard Error Plot of F-BSA During Treatment Period	FAS
4.3.2	Mean and Standard Error Plot of Change From Baseline in F-BSA During Treatment Period	FAS
4.3.3	Mean and Standard Error Plot of Percent Change From Baseline in F-BSA During Treatment Period	FAS
4.4.1	Mean and Standard Error Plot of T-BSA During Treatment Period	FAS
4.4.2	Mean and Standard Error Plot of Change From Baseline in T-BSA During Treatment Period	FAS
4.4.3	Mean and Standard Error Plot of Percent Change From Baseline in T-BSA During Treatment Period	FAS
4.5	Proportion of Participants Achieving VNS scores of 4 or 5 During the Treatment Period	FAS
4.6	Proportion of Participants Achieving an F PhGVA of Clear or Almost Clear During Treatment Period	FAS

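### The exposure-adjusted adverse-event tables pool the double-blind and extension periods, which dilutes ruxolitinib rates relative to vehicle for any event concentrated soon after starting treatment

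*SAP*

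**What the plan says.** SAP 8.1 plans the adjusted summaries: "In addition, summaries of exposure-adjusted TEAEs will be provided based on the actual treatment received". SAP 8.2.1 adds that they cover the safety population and include cumulative events. Appendix A lists four exposure-adjusted tables, 3.2.1.1.Y and 3.2.3.1.3.Y to 3.2.3.1.5.Y. The last is titled "Summary of Exposure-Adjusted Incidence Rates of Application Site Reactions With Vehicle Group by MedDRA Preferred Term in Decreasing Order of Frequency During the Treatment Period".

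The notes under the table list define the suffix Y as the two treatment periods combined, and add: "For participants who cross over, he/she should be included in both treatment groups". Three of the four titles name the vehicle group; for 3.2.1.1.Y the crossover note implies a vehicle column. Tables with the suffix X are given separately for the double-blind, extension and combined periods, but no X table is exposure-adjusted.

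On exposure:
- SAP 3.1: "Approximately 300 participants will be randomized 2:1 to receive initial study treatment (ruxolitinib cream 1.5% BID:vehicle) for 24 weeks".
- Protocol 4.1: "Participants initially randomized to vehicle will be crossed over to active drug". For vehicle, Protocol Table 9 has "Treatment extension period: Not applicable".
- SAP 1: extension participants "receive an additional 28 weeks of treatment extension with ruxolitinib cream 1.5% BID".
- Protocol 4.1: to enter the extension, a participant must also "be compliant with study procedures, and not have any safety issues".

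**The concern.** A rate per person-time compares groups with unequal follow-up fairly only if the hazard is roughly constant over that follow-up. Here follow-up is unequal by design. Vehicle time is all within 24 weeks of starting vehicle, while much of the ruxolitinib time is later. If an event type clusters near the start of treatment, the later time adds to the ruxolitinib denominator and brings few events with it. Application site reactions are a plausible example, and Table 3.2.3.1.5.Y is devoted to them.

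Selection at Week 24 is a second and separate issue. Extension time comes only from people judged compliant and free of safety issues. That also tends to lower the ruxolitinib rate.

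Safety and tolerability are a secondary objective. Read alone, the adjusted tables could make an early excess on ruxolitinib look smaller than it is, or absent.

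**Working it through.** The documents state no exposure-adjusted rate or person-time, so there is no planned figure of this kind to reproduce. The arm sizes can be checked. About 300 randomised 2:1 gives 200 and 100, and an exact Fisher calculation for 20% against 5% gives 96.6% power, close to the stated 95%.

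**Inputs from the documents.** 200 on ruxolitinib and 100 on vehicle; 24 weeks double-blind; 28 weeks extension; vehicle participants who continue switch to ruxolitinib and count in both groups.

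**Assumptions.** The same risk p on each treatment, with all events soon after first application. Crossovers carry that risk again when they start ruxolitinib. A fraction e enters and completes the extension. The documents give neither e nor event timing.

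**Formulae**, with rate = participants with an event / exposure time:
- Vehicle: 100p / (100 × 24 weeks)
- Ruxolitinib: (200p + 100e·p) / (200 × 24 + 200e × 28 + 100e × 28 weeks)

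With e = 1 these are 100p / 2,400 and 300p / 13,200 person-weeks, or 0.0417p and 0.0227p per week, a ratio of 0.545.

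With p = 5% (p cancels from the ratio), vehicle has 5 events in 46.2 person-years, or 10.8 per 100:

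| e | Ruxolitinib events | Ruxolitinib person-years | Rate per 100 | Ratio, all early | Ratio, half early |
|---|---|---|---|---|---|
| 100% | 15.0 | 253.8 | 5.9 | 0.55 | 0.77 |
| 90% | 14.5 | 237.7 | 6.1 | 0.56 | 0.78 |
| 80% | 14.0 | 221.5 | 6.3 | 0.58 | 0.79 |

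The last column is 0.5 × (all-early ratio) + 0.5 × 1, because events at a steady rate have a ratio of 1.

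**Sensitivity**
- Dropout of 0-20% by Week 24, a further 0-10% not entering and 0-10% dropout in the extension (all assumed): 0.545 to 0.584 if all events are early.
- Time stopped at first event, onset around week 2, p from 1% to 50%: 0.546 to 0.565.
- Crossovers with no new early risk, e = 1: (200p / 13,200) / (100p / 2,400) = 0.364.
- Constant hazard: 1 if time stops at first event. If full exposure time is used, 0.976 to 0.859 for 24-week risks of 5% to 30%. SAP 6.4 defines treatment duration, but the SAP does not say which rule applies to event rates.

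**Break-even.** 1/0.545 = 1.83 and 1/0.563 = 1.78. A true early excess of about 1.8-fold would appear as a ratio near 1.

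**Other tables, same scenario (e = 90%).** Crude whole-period tables: 14.5/290 = 5.0% against 5/100 = 5.0%. Crude double-blind tables: 10/200 against 5/100, again 5.0% each. Both show the correct null.

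**After the change (e = 1).** Double-blind only: 200p / 4,800 against 100p / 2,400, ratio 1.00. Whole-period ruxolitinib, first 24 weeks from first ruxolitinib application: 300p / (200 × 24 + 100 × 24) = 300p / 7,200 = 0.0417p per week, the vehicle rate.

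**The case against.** The strongest reply is that a like-for-like comparison is already planned. The X tables give crude percentages for the double-blind period, where planned exposure is 24 weeks per arm, and they include application site reactions (3.2.3.1.2.X). The crude Y tables also recover the right answer for early events. This stands, and it confines the fault to the four exposure-adjusted tables. A reader might infer that the plan would conceal an early excess. The documents do not support that: a 1.8-fold excess over a 5% risk would show as 9.0% against 5.0% in the double-blind crude tables.

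Second, nothing in the documents shows that events cluster early. Protocol 2.4.2.2.3 reports no significant application site events in Phase 2, and similar safety at Week 24 and Week 52. That evidence is qualitative and not about onset, but it means that a falling hazard is a possibility here and not an established fact.

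Third, a double-blind rate table is not ruled out. SAP 8.1 opens by promising its analyses for each period, SAP 8.2.2 lists adjusted rates without naming a period, and Appendix A calls itself a guideline. But no such table is listed, and these passages do not commit the sponsor to one.

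Finally, the SAP specifies no adverse-event hypothesis test and nowhere calls these tables fair comparisons. They are descriptive.

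**Conclusion.** The concern holds for the four exposure-adjusted Y tables. At equal risk their rate ratio would be about 0.55 to 0.58 if all events are early, 0.77 to 0.79 if half are, and about 1 under a constant hazard with time stopped at first event. The first two ranges assume that crossovers carry the same early risk when they start ruxolitinib.

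Two stronger readings should be resisted. One is that adverse-event rates in general will look about 45% lower on ruxolitinib. That figure needs every event to be early, and the documents give no timing. The other is that selection at Week 24 produces the 45%. It does not: the figure comes from unequal follow-up alone, and in this calculation non-entry slightly narrows the gap (0.545 to 0.563 when 10% do not enter). With full retention 4,800 of the 13,200 ruxolitinib person-weeks (36%) precede the selection, and crossovers were selected while on vehicle. The selection bias acts in the same direction but cannot be sized from the documents.

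No efficacy analysis or double-blind safety table is affected. This is a cheap improvement to descriptive safety reporting.

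**What to change.** Amend SAP 8.1, 8.2.1 and Appendix A as follows:
- Base the exposure-adjusted comparison with vehicle (3.2.1.1.Y and 3.2.3.1.3.Y to 3.2.3.1.5.Y) on the double-blind period.
- Report whole-period ruxolitinib exposure-adjusted rates split into weeks 0-24 and after week 24, counted from first ruxolitinib application.
- Footnote that the later time comes from participants selected at Week 24. For crossovers this applies to all their ruxolitinib time.

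The cost is SAP and table-shell wording and minor extra programming, with no new data. The vehicle comparison would use less ruxolitinib time: 4,800 instead of 13,200 person-weeks with full retention.

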8.2. Adverse Events

8.2.1. Adverse Event Definitions

A TEAE is any AE either reported for the first time or worsening of a pre-existing event after first application of study drug and within 30 days of the last dose of study drug. For participants who cross over treatments, the first application date is period-specific, and the end date is 30 days after the last application date in this period, or the first application date in the next period, whichever comes first. Analysis of AEs (as discussed below) will be limited to TEAEs,

but data listings will include all AEs regardless of their timing in relation to study drug application.

Adverse events will be tabulated by MedDRA PT and SOC. Severity of AEs will be graded using the NCI CTCAE. The CTCAE v5.0 is used for this study. The CTCAE reporting guidelines and grading details are available on the Cancer Therapy Evaluation Program website.

The subset of AEs considered by the investigator to be related to study drug will be considered to be treatment-related AEs. If the investigator does not specify the relationship of the AE to study drug, the AE will be considered to be treatment-related. The incidence of AEs and treatment-related AEs will be tabulated. Serious AEs will also be tabulated.

Any missing onset date, causality, or severity must be queried for resolution. Unresolved missing causality and severity will be handled according to the following rules:

- An unresolved missing causality will be considered treatment-related.
- An unresolved missing severity will be identified as an unknown severity.

For purposes of analysis, all AEs will be considered TEAEs unless the AE can unequivocally be defined as not treatment-emergent.

Application site reactions are AEs that occur at the site of drug application. A summary of ASRs will be provided. Exposure-adjusted summaries will be provided for the safety population including cumulative TEAEs.

